6.2 Secondary Efficacy Objective

The secondary efficacy objective is to demonstrate that the group mean sentence recognition score with the EAS system in quiet at twelve months after first fitting is 40% or better.

Subsidiary objectives include:

- Observation of the evolution of the mean monosyllabic word recognition score with the EAS system in quiet at 6, 12 months, 2, 3, 4 and 5 years after first fitting and more if available
- Observation of the evolution of the mean sentence recognition score with the EAS system in quiet at 6, 12 months, 2, 3, 4 and 5 years after first fitting and more if available
- Observation of the evolution of the mean sentence recognition score with the EAS system in noise at 6, 12 months, 2, 3, 4 and 5 years after first fitting and more if available.

There are no safety objectives for this clinical investigation. Safety events will not be collected retrospectively for the included subjects.

7.0 Study Protocol

7.1 Subject Population and Selection Criteria

7.1.1 Number of subjects

As a retrospective analysis, this study will include all patients fulfilling inclusion and exclusion criteria and registered in the clinical patient database at the time of the extraction of the data. Considering the EAS population already implanted at MHH since January 2017 (estimated at 50 users) and based on the estimation of patients who provided informed consent and who fulfill the inclusion criteria, the size of the included population is estimated to be around 30 to 40 subjects.

Any CI recipient from the implicated center (MHH in Hanover, Germany) implanted with an Ultra or an Ultra 3D implant and meeting the below defined inclusion criteria will be included.

7.1.2 Description of procedures for the selection of subject

This analysis only includes observational retrospective analyses of clinical data. Data related to all eligible subjects will be queried from the clinical patient database.

7.1.3 Inclusion Criteria

- Being implanted with Ultra or Ultra 3D SlimJ
- Being a user of the "acoustic earhook" system
- Having provided informed consent regarding use of his/her data for research.

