1.0 Synopsis

Study Title	Retrospective analysis of long-term speech performance in cochlear implant recipients using electro-acoustic stimulation
Sponsor	Advanced Bionics AG
Investigational Device	Naída CI M and Naída CI Q and associated acoustic earhooks
Study Design	A monocentric observational post-market clinical follow-up study (PMCF) based on a retrospective data analysis of anonymized clinical data
Study Population	All subjects fulfilling inclusion and exclusion criteria and registered in clinical patient database at the time of the extraction of the data
Inclusion Criteria	Being implanted with Ultra or Ultra 3D SlimJ Being a user of the "acoustic earhook" system Having provided informed consent regarding use of his/her data for research
Exclusion Criteria	N/A
Primary Study/Efficacy Objective	Mean monosyllabic word recognition score with the EAS system in quiet at twelve months after first fitting of 30% or better
Primary Study/Efficacy Endpoint	Group average on the Freiburger Monosyllabic Word Test (in quiet) of 30% or more at twelve-month after first fitting
Secondary Study/Efficacy Objective	Mean sentence recognition score with the EAS system in quiet at twelve months after first fitting of 40% or better
Secondary Study/Efficacy Endpoint	Group average in the HSM sentence test (in quiet) of 40% or more at twelve-month after first fitting
Safety Objective	N/A
PMCF Objective (if required)	Collection of additional clinical data on acoustic earhook performance
Study Schedule & Duration	Estimated time for data collection, analysis and writing of the report: 3 months

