5.4 Description of the clinical development stage

Not applicable, all devices under investigation are CE-marked.

5.5 Description of the measures taken to minimize or avoid bias, including randomization and blinding/masking

The cohort shall reflect the general population and represent real world data. The subjects are not selected, fulfillment of all inclusion criteria is the one condition. Factors such as gender or lifestyle are not expected to have an effect on study outcomes. By selecting all eligible subjects from the clinic's database in the analysis, selection bias is minimized.

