7.1.5 Anticipated distribution of enrolment and period of enrolment

This section is not applicable, this is a retrospective observational study for which data are already collected. Patients implanted between January 2017 and August 2022 and fulfilling above selection criteria will be included.

Only one expert center will be part of this study. The center enrolled all patients.

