7.2 Study Endpoints

7.2.1 Primary Efficacy endpoint

The primary efficacy endpoint is the group mean Freiburger Monosyllabic Word score (in quiet) of 30% or more at twelve months after the first fitting.

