8.2 Statistical Design & Data Analysis

8.2.1 Analytical procedures

Data will be analyzed using descriptive statistics and further analyses might be performed using applicable parametric or nonparametric methods, depending on the number of available datasets.

The study plans to screen up to 50 patients. Among these 50 potential subjects, based on the estimation of patients who provided informed consent and who fulfill the inclusion criteria, the size of the included population is estimated to be around 30 to 40 subjects.

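### The earhook criterion is undated; read literally at database query, it makes eligibility depend on continued use after month 12 and may bias the mean, probably upward

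*Combined protocol and SAP*

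**What the plan says.** The earhook criterion in section 7.1.3 is "Being a user of the 'acoustic earhook' system". It has no time point, minimum duration or definition. The consent criterion in the same list is worded as something already done; the earhook criterion is worded as a current state.

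The Synopsis defines the population as "All subjects fulfilling inclusion and exclusion criteria and registered in clinical patient database at the time of the extraction of the data", and section 7.1.1 has similar wording. Section 7.1.5 adds: "Patients implanted between January 2017 and August 2022 and fulfilling above selection criteria will be included". No extraction date is given.

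Section 7.1.1 puts the EAS population at the centre at about 50, already described as users. Section 8.2.1 expects that "the size of the included population is estimated to be around 30 to 40 subjects", after consent and the inclusion criteria.

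On bias, section 5.5 states: "The subjects are not selected, fulfillment of all inclusion criteria is the one condition". It concludes that taking all eligible subjects minimises selection bias. Section 7.1.4 describes an exhaustive approach. Sections 7.3.6 and 7.3.7 discuss only the single centre and the lack of source verification as threats.

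The primary endpoint is the "group mean Freiburger Monosyllabic Word score (in quiet) of 30% or more at twelve months after the first fitting". Section 6.1 makes clear that this is the score with the EAS system.

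**The concern.** An implant is permanent, but earhook use is not. A patient may be fitted, be tested with the earhook at month 12, and stop later, for example because residual hearing is lost or the benefit is small. If the person querying the database takes the criterion literally, that patient is not a user and the 12-month score is lost. Inclusion would then depend on something that happens after the endpoint and may well be related to it.

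The long-term curves in section 6.2 are exposed in the same way: a patient who stops in year 3 would also lose the scores from month 6 to year 2.

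The pass/fail rule in sections 8.2.2 and 8.2.3 compares a bare mean with 30%, without an interval or a test, so near the threshold a shift of a few points decides the outcome. It would also be hard to detect afterwards. The data list in section 14.3 has no item labelled as earhook start or stop, none for whether the earhook was worn at a test, and no visit-level audiometry. Tests used the processor in its usual setting (section 7.3.2). The sponsor cannot verify source data (section 14.1), and the spreadsheet is deleted once the report is final (section 14.8).

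**Working it through.** **1. Figures in the plan.** There is no power calculation to reproduce. The expected inclusion is 30/50 = 60% to 40/50 = 80%, so 10 to 20 of the 50 are not included. The plan attributes this to consent and eligibility together and does not split it. No stopping rate, reason for stopping, score for stoppers or expected mean is given.

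**2. What is dated.** The extraction phrase in section 7.1.1, "registered in the clinical patient database at the time of the extraction of the data", dates registration in the database. Nothing dates earhook use: not first fitting, not month 12, not extraction.

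**3. Possible gap between endpoint and extraction.** Assume first fitting about 1 month after implantation. A patient implanted in January 2017 reaches month 12 about 4.5 years before the end of August 2022. A patient implanted in August 2022 reaches it in about September 2023. The gap is therefore years for early implants and cannot be determined for late ones without the extraction date.

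**4. Who is avoidably lost.** Patients who stopped before month 12 may have no 12-month score with the EAS system under any wording of the criterion. The avoidable loss is of patients who were tested with the earhook at month 12 and stopped later.

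**5. Size of the shift.** Let d be the share of patients with a 12-month EAS score who later stopped, U the mean of continuing users and S the mean of stoppers. The mean of all is (1 − d)U + dS, so

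shift = U − [(1 − d)U + dS] = d × (U − S).

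All inputs below are assumed.

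| d | U − S (points) | Shift (points) |
|---|---|---|
| 5% | 10 | 0.5 |
| 10% | 10 | 1.0 |
| 20% | 10 | 2.0 |
| 20% | 20 | 4.0 |
| 40% | 20 | 8.0 |
| any | 0 | 0 |
| 5% | −10 | −0.5 |
| 40% | −10 | −4.0 |

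The 40% is an extreme value: it is what would follow if all 20 non-included patients (20/50) were stoppers. It is not a strict bound, because the count of 50 may itself already omit stoppers.

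**6. Relation to the threshold.** The users-only mean exceeds 30% while the mean of all is at or below 30% whenever U lies above 30 and at or below 30 + d × (U − S). With d = 20% and a 20-point gap, the upper limit is 30 + 0.20 × 20 = 34%. As one illustration, U = 33, S = 15 and d = 20% give 0.8 × 33 + 0.2 × 15 = 26.4 + 3.0 = 29.4%. The documents do not suggest that the mean will lie in this range.

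**The case against.** The strongest reply is that the criterion may simply mean patients who were ever fitted. Section 7.1.1 calls the whole implanted EAS population users, which reads like a cohort label. Section 7.1.4 aims to be exhaustive, and sections 7.1.7 and 14.3 count follow-up from first fitting. On that reading nobody is lost. This stands as a possible reading, but the text does not settle it. Centre staff must check eligibility in the database (section 4.9) without a rule, so two people could extract two different cohorts.

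A reader might infer that the plan judges earhook use at extraction. The documents do not say so; the extraction wording attaches to database registration. A reader might also infer that section 5.5 is contradicted. It is not, strictly: taking everyone who meets the criteria agrees with its wording. Section 5.5 is silent on stopping, which is a gap and not a contradiction.

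It is also fair to object that patients who stopped after month 12 were still users when tested, and nothing in the documents shows that they scored 10 or 20 points lower at that time. This stands and is why the size is given only as a range that includes zero and negative values.

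Finally, putting every ever-fitted patient's 12-month score into the primary mean would change the target, because section 6.1 asks for the score with the EAS system. This is accepted, and the fix below keeps to that objective.

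**Conclusion.** The point holds in conditional form. The criterion is undated, and its literal reading at database query conditions eligibility on continued use after the endpoint. The 12-month mean and the long-term curves may then be biased. Upward is the likelier direction, if patients stop because of poor benefit or lost hearing, but the documents do not establish it. Under the assumed 5% to 40% stopped and a 10 to 20 point deficit, the shift is 0.5 to 8 points; with equal scores it is zero, and with stoppers scoring higher it is negative.

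It would go too far to say that the bias is certain or that the pass/fail result will flip. A flip needs a mean close to 30% as well as a sizeable gap, and the plan gives no information on either. The change should nevertheless be made before extraction, since it costs little and the effect could not be checked later from the listed data.

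**What to change.** 1. Reword the criterion in section 7.1.3 and the Synopsis to: was fitted with an acoustic earhook at any time, for patients implanted from January 2017 to August 2022.
2. Base the primary mean on every 12-month score obtained with the EAS system, whatever the later use. Add a sensitivity analysis that also includes ever-fitted subjects tested at month 12 without the earhook.
3. Add to the section 14.3 list, where the database holds them, earhook start and stop dates, whether the earhook was worn at each test, and the pure-tone thresholds that Table 9 shows as routine.
4. Report the numbers fitted, consented, stopped before month 12, stopped later, and with a 12-month score.

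The cost is one reworded criterion, a few extra columns and a flow table. Some of the columns may be incomplete in routine records, and the mean may turn out slightly less favourable.

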7.1.4 Exclusion criteria

There are no specific exclusion (and non-inclusion) criteria, all patients fulfilling inclusion criteria described above and registered in the clinic patient database will be included.

The absence of exclusion criteria is based on the intention to have an exhaustive approach. By eliminating all restrictions, it is expected to include a representative range of participants, thereby maximizing the generalizability of the results to the general population.

7.1.5 Anticipated distribution of enrolment and period of enrolment

This section is not applicable, this is a retrospective observational study for which data are already collected. Patients implanted between January 2017 and August 2022 and fulfilling above selection criteria will be included.

Only one expert center will be part of this study. The center enrolled all patients.

7.1.6 Point of randomization

There is no randomization as this is a retrospective observational study on data collected during clinical routine.

7.1.7 Expected duration of each subject participation

This section is not applicable. This is a retrospective observational study on data already collected with no further subject participation required. Subjects with follow-up up to 5 years after first fitting of the Naída CI Q or Naída CI M sound processors and associated earhooks can be included.

7.1.8 Total expected duration of the study

This is a retrospective observational study on data already collected. The duration of the investigation corresponds to the time needed to analyze the data, prepare the report, and fulfill any regulatory requirement, as applicable. A total of 3 months is estimated to analyze the data and prepare the report.

7.2 Study Endpoints

7.2.1 Primary Efficacy endpoint

The primary efficacy endpoint is the group mean Freiburger Monosyllabic Word score (in quiet) of 30% or more at twelve months after the first fitting.

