
CI-5280 (Naída CI Q90 Sound Processors)
 
Undesirable side effects of Naída CI system may include skin irritation and discomfort from pressure on the ear, device overheating, or overly loud sounds. If any undesirable side effect is encountered, please remove your sound processor and consult your cochlear implant professional.
 
CI-5850 (Naída CI Q90 Acoustic Earhook)
 
Undesirable side effects of Naída CI system may include skin irritation and discomfort from pressure on the ear, device overheating, or overly loud sounds
 
CI-5293-xxx (Naída CI M90), CI-5295-xxx (Sky CI M90), CI-5851-xxx (M Acoustic Earhook)
 
Undesirable side effects of your Marvel CI sound processor and accessories may include skin irritation and discomfort from pressure on the ear, device overheating, or overly loud sounds. If any undesirable side effect is encountered, please remove your sound processor and consult your cochlear implant professional.
	
Claimed clinical benefit	

The intended clinical benefit of the Naída CI Sound Processor and Accessories as part of the HiRes™ Bionic Ear System is defined as:
 
 For adults: 
 Word recognition score in quiet higher or equal to 30% at a minimum of 12 months follow-up OR improvement higher than 30% compared to pre-operative stage AND/OR Sentence recognition score in quiet higher or equal to 40% at a minimum of 12 months follow-up OR improvement higher than 40% compared to pre-operative stage For children: 
 Before 4 years old: auditory awareness higher than 50% at a minimum of 12 months follow-up Above 4 years old: word/sentence recognition in quiet higher than 30% or improvement of 30% at a minimum of 12 months follow-up. 	
Expected lifetime	
CI-5280-xxx - Naída CI Q90	5 years
CI-5850-xxx - Naída CI Q90 Acoustic Earhook	1 year
CI-5293-xxx (Naída CI M90) CI-5295-xxx (Sky CI M90)	5 years
CI-5851-xxx (M Acoustic Earhook)	1 year
Invasiveness	
Non-invasive (external)	
Contact duration	
Intact skin, >30 days	
Type of use	

Single-use*	
Sterile	
Non-sterile	
Novel product	
	YES
x	NO
Novel related clinical procedure	
	YES
x	NO
Explanation of any novel features	
N/A	

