6.0 Objectives

6.1 Primary Efficacy Objective

The primary efficacy objective is to demonstrate that the group mean monosyllabic word recognition score with the EAS system in quiet at twelve months after first fitting is 30% or better. This efficacy outcome has been defined in accordance with the State-Of-The-Art (SOTA) performed by AB, and claimed clinical benefits for the HiRes Bionic Ear System from AB.

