7.2.2 Secondary Efficacy endpoint

The secondary efficacy endpoint is the group mean HSM score (in quiet) of 40% or more at twelve months after the first fitting.

Subsidiary efficacy endpoints include:

- The mean monosyllabic word recognition score with the EAS system in quiet at 6, 12 months, 2, 3, 4 and 5 years after the first fitting
- The mean sentence recognition score with the EAS system in quiet at 6, 12 months, 2, 3, 4 and 5 years after the first fitting
- The mean sentence recognition score with the EAS system in noise at 6, 12 months, 2, 3, 4 and 5 years after the first fitting.

Regarding the sentence recognition score, either HSM sentence test or the OISa recognition score were collected during the clinical routine. The center initially collected the HSM sentence test routinely and then switched to the OISa recognition score. Therefore, throughout follow-up the speech test used to evaluate performance may have changed. Regarding the secondary objective and associated endpoint, the HSM sentence test will be used.

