8.2.2 Primary efficacy hypothesis

The primary efficacy hypothesis is based on the total number of subjects n and score (percentage of words correctly understood) in the Freiburger Monosyllabic Word Test twelve months after the first fitting.

Thus, the primary efficacy hypothesis is:

$$\frac{\sum(\text{Word Score 12 months})}{N} > 30\%$$

With:

Word Score 12 months = % of words correctly recognized at 12 months after the first fitting

N = number of datasets

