8.2.3 Secondary efficacy hypothesis

The second efficacy hypothesis is based on the total number of subjects n and score (percentage of words correctly understood) in the HSM sentence test in quiet and in noise one year post activation.

Thus, the secondary efficacy hypothesis is:

$$\frac{\sum(HSM \text{ Score } 12 \text{ months})}{N} > 40\%$$

With:

HSM Score 12 months = % of correct sentence recognized at 12 months in quiet and in noise after the first fitting

N = number of datasets

- **Pass/fail criteria to be applied to the results of the clinical investigation**

The primary efficacy hypothesis needs to be fulfilled in order to consider this investigation successful.

- **Procedure for reporting any deviation(s) from the original statistical plan**

In case of a deviation from the statistical plan, the final report will highlight and justify the deviations.

- **Minimum and maximum number of subjects to be included for each center in multicenter clinical investigations**

This section is not applicable. The study is a monocentric study.

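### The primary endpoint is met at a mean word score of 30% or more, but the hypothesis that decides success needs a mean strictly above 30% (minor)

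*Combined protocol and SAP*

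**What the plan says.** The primary bar is stated inclusively in three places. The Synopsis gives the endpoint as "Group average on the Freiburger Monosyllabic Word Test (in quiet) of 30% or more at twelve-month after first fitting". Section 6.1 words the objective as "group mean monosyllabic word recognition score with the EAS system in quiet at twelve months after first fitting is 30% or better". Section 7.2.1 repeats the inclusive bar as the formal endpoint, a "group mean Freiburger Monosyllabic Word score (in quiet) of 30% or more at twelve months after the first fitting". Section 6.1 also ties the outcome to the claimed clinical benefit, and for adults Table 4 (Section 4.4) words that claim as "Word recognition score in quiet higher or equal to 30% at a minimum of 12 months follow-up"; Section 12.2 has an equivalent line.

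Section 8.2.2 then writes the primary hypothesis as a formula: the sum of the 12-month word scores divided by N is greater than 30%, with a strict sign. Under Section 8.2.3 the pass/fail clause reads: "The primary efficacy hypothesis needs to be fulfilled in order to consider this investigation successful".

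For sentences, Section 7.2.2 states: "The secondary efficacy endpoint is the group mean HSM score (in quiet) of 40% or more at twelve months after the first fitting". The Synopsis and Section 6.2 agree with it, but the formula in Section 8.2.3 has the mean strictly greater than 40%.

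**The concern.** The plan has one binary conclusion, and it rests on a point estimate set against a threshold. Section 8.2.1 plans descriptive statistics, with no significance level or confidence interval. The inequality sign is therefore a large part of the decision rule, and it differs between the objective and endpoint on one side and the criterion that decides success on the other. A report on a mean of exactly 30% would have to say that the primary objective was met and that the investigation failed. Nothing in the plan resolves this, and no rounding convention is given for the mean.

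**Working it through.** The plan states no SD, power or calculated sample size, so there is no figure of its own to reproduce. The check has two parts.

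**1. The statements side by side**

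| Place | Word score | Sentence score | Decides success? |
|---|---|---|---|
| Synopsis | mean ≥ 30% | mean ≥ 40% | no |
| 6.1 / 6.2 (objectives) | mean ≥ 30% | mean ≥ 40% | no |
| 7.2.1 / 7.2.2 (endpoints) | mean ≥ 30% | mean ≥ 40% | no |
| 8.2.2 / 8.2.3 (hypotheses) | mean > 30% | mean > 40% | word score only |

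Take N = 35 and scores in 5-point steps. A score total of 1,050 gives 1,050/35 = 30, which meets ≥ 30 and fails > 30. The neighbouring totals give the same answer under both signs: 1,045/35 = 29.86 fails both, and 1,055/35 = 30.14 passes both. The disagreement is confined to exact equality.

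**2. How likely is exact equality?**

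Inputs: N = 30 to 40 (Sections 7.1.1 and 8.2.1). Assumptions not in the documents: between-subject SD of 15, 20 or 25 points; score step of 1, 2.5 or 5 points.

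The mean moves in steps of step/N and has standard error SD/√N. If the true mean sits on the threshold, the normal approximation is

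P(tie) ≈ (step/N) / (SE × √(2π)) = step / (SD × √N × 2.507)

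- Central case (N = 35, SD 20, step 5): 5 / (20 × 5.916 × 2.507) = 1.7%.
- Largest (N = 30, SD 15, step 5): 5 / (15 × 5.477 × 2.507) = 2.4%.
- Smallest (N = 40, SD 25, step 1): 1 / (25 × 6.325 × 2.507) = 0.25%.

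An exact calculation (repeated convolution of a discretised beta distribution of scores) gives the same 0.25% to 2.4% range. In the central case the chance of passing at a true mean of 30% is 48.5% under > and 50.1% under ≥, a gap of 1.7 points before rounding.

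Away from the threshold, P(tie) is multiplied by exp(−d²/(2 SE²)), where d is the distance of the true mean from 30. In the central case at a true mean of 40%, SE² = 400/35 = 11.43, so the factor is exp(−100/22.86) = 0.0126 and P(tie) ≈ 0.02%. Over the whole grid the exact results are 0.04% to 0.83% at a true mean of 35% and at most 0.13% at 40%.

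For the 40% sentence threshold the exact figures are similar: 0.25% to 2.4% at a true mean of 40%, and 0.05% to 0.81% at 45%.

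**The case against.** The best answer is that this is editorial. Section 8.2.3 names a single success criterion, the primary hypothesis, and the endpoint wording has no pass/fail role. That much stands. A reader might infer that the plan contains two rival success rules, but it contains one, which does not match the objective and endpoint it is meant to decide. The same clause invokes only the primary hypothesis, so the 40% mismatch cannot change whether the study succeeds.

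A reader might also infer a much larger effect by assuming that the mean is rounded to a whole percent before comparison. The signs would then disagree for any mean from 29.5 up to 30.5. With SE = 20/√35 = 3.38 that is 2Φ(0.5/3.38) − 1 ≈ 12% at a true mean of 30%. The arithmetic is right, but no section describes such rounding, so the figure is not an effect of the stated rules. What remains is that the plan does not exclude rounding, and one sentence would do so.

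It is tempting to add that the sponsor, who analyses the data (Section 7.3.5), would choose the convenient reading once the mean is known. The documents do not support this: Section 8.2.3 fixes the criterion on the hypothesis and requires deviations from the statistical plan to be highlighted and justified.

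The benefit claim does not point wholly one way either. Table 4 and Section 12.2 are inclusive for adults, but for children above 4 years they require a score strictly higher than 30%, and Section 11.0 sets no age limit. The claim also offers improvement over the pre-operative score as an alternative and is not worded as a group mean. So the strict sign cannot simply be dismissed as a slip.

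Finally, the contrary evidence is one character in each of two formulas, where a lost bar under the sign would dissolve the point. Both formulas agree, and ≥ survives in the indications in Table 4, so this is a reason to check the printed formulas rather than an answer.

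**Conclusion.** The inconsistency is real and minor. The objective and primary endpoint are satisfied at a mean of exactly 30%, and the sole success criterion is not. The sentence outcome repeats the mismatch at 40% without consequence for study success. On the unrounded mean the chance that it matters is about 0.25% to 2.4% in the worst position, a true mean of 30%, and about 0.1% or less at 40%. These figures depend on the assumed SDs and score steps and on the plan's expected 30 to 40 subjects. The point deserves correction because it lies in the study's only decision threshold, not because it is likely to change the result.

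Aligning the signs leaves two neighbouring matters untouched: the criterion has no test or interval behind it, and the secondary hypothesis in Section 8.2.3 covers quiet and noise while its endpoint covers quiet only.

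**What to change.** In Sections 8.2.2 and 8.2.3, replace > by ≥ in both formulas, so that they match the Synopsis, Sections 6.1, 6.2, 7.2.1 and 7.2.2, and the adult benefit claim. Add one sentence stating that the unrounded group mean is compared with the threshold. If the sponsor does intend a strict bar, the Synopsis, objectives and endpoints should be changed instead; either way one sign should be used throughout. The strict wording of the claim for children above 4 years should be acknowledged where the thresholds are justified.

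The cost is two symbols and one sentence, handled under the amendment procedure in Section 16.1 before the 12-month means are calculated. No new data or analysis is needed.
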